### 1.3.2 Toxicology

Six-week and 6-month Good Laboratory Practice (GLP) repeat-dose toxicity studies were conducted in cynomolgus monkeys and a definitive GLP embryo-fetal development study was conducted in New Zealand White rabbits. The intravenous (IV) route of administration was selected for these studies since it is the route of clinical administration. In addition, a series of in vitro studies were conducted with PRA023 including Fc effector function (i.e., antibody-dependent cellular cytotoxicity [ADCC] and complement-dependent cytotoxicity [CDC], and antibody-dependent phagocytosis cytotoxicity [ADCP]) assays, human cytokine release assays, and a GLP tissue cross-reactivity study using human and monkey tissues.

Stand-alone safety pharmacology studies were not conducted with PRA023. Cardiovascular, central nervous system (CNS), and respiratory safety pharmacology endpoints were incorporated into the repeat-dose IV toxicity studies in monkeys. There were no functional cardiovascular, CNS or respiratory system findings observed in monkeys after once weekly IV administration of PRA023 at  $\leq 300$  mg/kg/week for up to 6 months.

PRA023 was administered to monkeys once weekly via IV injection for up to 6 months. The no observed adverse effect level (NOAEL) in the 6-month study was considered to be 300 mg/kg/week (the highest dose tested). No PRA023-related mortality; adverse clinical observations; body weight or body weight alterations; hematology, coagulation, or urinalysis effects; organ weight effects; macroscopic observations; microscopic findings; ECG findings; ophthalmic or neurobehavioral observations or findings in body temperature or respiration rates were observed at the end of the dosing phase after 6 months of repeat dosing in monkeys. No PRA023-related effects were noted in mean absolute counts or relative proportions of lymphocyte subsets (total T cells, helper and cytotoxic T cells, B cells, NK cells, monocytes, and regulatory helper and cytotoxic T cells) at  $\leq 300$  mg/kg/week as measured by immunophenotyping, compared with the controls. All animals mounted a robust anti-KLH IgG and IgM response, suggesting an intact humoral immunity. There were no organ weight changes, or macroscopic or microscopic observations in male or female reproductive organs after 6 months repeat dosing of PRA023 administration in sexually mature monkeys. A normal progression of the spermatogenic cycle and the expected cell associations and proportions in the various stages of spermatogenesis were noted in the testes.

After IV administration of PRA023 to monkeys in the 6-week repeat-dose toxicity study, findings that were secondary to generation of ADA and immune complex deposition in response to administration of a foreign protein (humanized monoclonal antibody) to immunocompetent animals (including the death of one low dose animal) were observed. Similar findings were not observed in the 6-month monkey toxicity study using the same dosing regimen and dose levels confirming that the findings in the 6-week repeat-dose toxicity study were secondary to ADA formation and not directly related to the mechanism of action of PRA023.

Based on the NOAEL of 300 mg/kg/week, the exposure margin (based on area under the curve from 0 to 168 hr [AUC0-168hr] on repeat dosing; [REDACTED] μg\*hr/mL) at the NOAEL is [REDACTED]-fold, relative to the projected AUC0-672hr ([REDACTED] μg\*hr/mL) after the last 500 mg induction dose (i.e., highest predicted exposure due to accumulation with repeat dosing) in the dosing regimen. Similarly, for maximum concentration (Cmax), the exposure margin (based on Cmax after repeat dosing; [REDACTED] μg/mL) at the NOAEL is [REDACTED]-fold, relative to the projected exposure ([REDACTED] μg/mL) after the last 500 mg induction dose.

In the pivotal EFD study, once-weekly administration of 50, 150, or 270 mg/kg/dose PRA023 via intravenous injection to pregnant rabbits on gestation days (GDs) 7 and 14 was well tolerated. No PRA023-related mortality, clinical observations, or effects on mean body weight gain, mean body weight, food consumption, or cesarean section parameters were observed during the period of organogenesis. (GD7 through 19). No PRA023-related fetal external, visceral, or skeletal variations or malformations were observed. The maternal and fetal no observed adverse effect levels (NOAELs) are [REDACTED] mg/kg/dose (Cmax of [REDACTED] μg/mL and AUC0-inf of [REDACTED] μg\*hr/mL). The exposure margins, based on Cmax and AUC0-inf, at the NOAEL are [REDACTED] and [REDACTED]-fold, respectively, relative to the projected clinical exposures after the last 500 mg induction dose.

There was no off-target binding of PRA023 noted in the tissue cross-reactivity study in a broad range of human or monkey tissues. There was no PRA023-related cytokine release in in vitro human PBMC or whole blood cytokine release assays (soluble and plate-bound formats), nor in monkeys during the 6-week repeat-dose toxicity study. PRA023 did not cause CDC, ADCC, or ADCP of target expressing cells in in vitro Fc effector function assays.

## 1.4 Previous Human Experience

A single and multiple ascending dose Phase 1 study of PRA023 in healthy volunteers has been completed. In this study, doses ranging from 5 mg to 1000 mg given as a single dose or three multiple doses given every two weeks were evaluated (Study PR200-101).

A total of 69 healthy subjects completed the dosing phase, 46 subjects in single ascending dose (SAD) phase (35 subjects received active PRA023 and 11 subjects received placebo) and 23 in the multiple ascending dose (MAD) phase (17 subjects received PRA023 and 6 subjects received placebo) in Study PR200-101. In the SAD phase, doses of PRA023 tested were 5 mg, 25 mg, 100 mg, 300 mg, 600 mg, and 1000 mg given as a single IV infusion. In the MAD phase, doses of PRA023 tested were 50 mg, 200 mg, and 500 mg given as an IV infusion every 2 weeks for a total of 3 doses. No clinically significant treatment-related adverse events were reported and no clinically significant laboratory abnormalities, vital signs, or ECGs were noted with PRA023, at doses up to 1000 mg as a single dose and 500 mg as multiple doses. The study drug was well-tolerated, and no subjects met the study stopping criteria.

### 1.4.1 Pharmacokinetic Results (PR200-101 Healthy Volunteer Study)

PK data from the PR200-101 study indicate that the exposure to serum PRA023 increased in a greater than dose-proportional manner following the administration of single and multiple PRA023 doses as IV infusions at doses of < 100 mg; the exposure increases at doses of  $\geq$  100 mg were dose-proportionate. This observation is consistent with target mediated drug disposition (TMDD) at lower doses (< 100 mg). The half-life of PRA023 after 500 mg every other week dosing was approximately 19 days.

Based on the preliminary PK data available, a population PK model was built to accurately simulate and predict PRA023 PK. The PK data were best described by a 2-compartment model with linear elimination. Demographic variables (including sex, age, race, and body size related variables) and laboratory clinical variables (including hematological, urine, and chemical variables) were tested for inclusion in the model for effect on the clearance and the volume of distribution in the central compartment. None of these variables were identified as significant covariates on the two PK parameters evaluated. The results of these analyses are presented in the Investigator's Brochure for PRA023. Briefly, evaluation of the model relative to observed data from the healthy volunteer study indicated that the population PK model could adequately predict the observed PRA023 concentrations and was suitable to be used to simulate PRA023 concentrations.

### 1.4.2 Safety Results

Study PR200-101 has been completed. There were no deaths, SAEs, severe AEs, or subjects who had a reduction in dose or discontinued from the study due to AEs during Study PR200-101. Additionally, there were no clinically significant laboratory abnormalities, vital signs, or ECGs.

In the SAD, treatment-emergent AEs that occurred in  $\geq$  2 subjects dosed with PRA023 (regardless of dose) were: headache (5 subjects [14%] in PRA023 and 1 subject [9%] on placebo), followed by fatigue (2 subjects [6%] on PRA023, 0 on placebo), back pain (2 subjects [6%] on PRA023, 0 on placebo), and cough (2 subjects [6%] on PRA023, 0 on placebo). All other AEs were reported in no more than 1 subject. There was 1 event of headache that was assessed as related to placebo that was moderate in severity. The only other AE that was assessed as related to PRA023 (600 mg) was somnolence, mild in severity.

In the MAD portion of the study, treatment-emergent AEs that occurred in  $\geq$  2 subjects dosed with PRA023 (regardless of dose) were: catheter site bruise (3 subjects [18%] on PRA023, 2 [33%] on placebo), followed by catheter site pain (2 subjects [12%] on PRA023, 1 [17%] on placebo), and infusion site extravasation (2 subjects [12%] in PRA023, 0 in placebo). All other AEs were reported in no more than 1 subject. All AEs that were assessed as related to study drug were mild in severity. Of the AEs assessed as related to study drug by the Investigator, diarrhea was reported in 2 subjects (1 subject on PRA023 at 50 mg and 1 subject on placebo) and all other AEs (dizziness [PRA023 200 mg], headache [placebo], and somnolence [PRA023 50 mg]) were reported in 1 subject.

For the ongoing Phase 2 studies PR200-102 ARTEMIS-UC (this protocol) and PR200-103 APOLLO-CD, ongoing review of unblinded efficacy and safety data by the Data Monitoring Committee (DMC) has resulted in the committee's recommendation to continue the study, Subjects from the ARTEMIS-UC study have been dosed for up to 10 months (i.e., either 10 months of PRA023 or 3 months of placebo followed by 7 months of PRA023) and subjects from the APOLLO-CD (open-label) study have been dosed for up to 9 months of PRA023 as of the date of this protocol amendment.

## 1.5 Dose Rationale

PRA023 is a humanized monoclonal antibody that binds human TL1A. It is expected that the ultimate goal of PRA023 treatment in humans will be to saturate the TL1A target in intestinal/colonic tissue of disease patients to obtain optimal efficacy. Based on the emerging safety, tolerability, pharmacodynamic (PD) and PK data from the PR200-101 study and modeling, the dosing regimen selected for induction in this study is PRA023 1000 mg on Week 0/Day 1 followed by 500 mg on Weeks 2, 6, and 10, administered intravenously. This regimen is expected to lead to optimal target modulation and confer pharmacologic efficacy. The NOAEL in monkeys will provide a safety margin of ~[redacted]-fold and ~[redacted]-fold for  $C_{max}$  and  $AUC_{0-672hr}$ , respectively, after the last 500 mg induction dose (i.e., highest predicted AUC due to accumulation with repeat dosing) in this dosing regimen.

A population PK model was built based on the available data from Study PR200-101. The model was adequate to predict and simulate PRA023 exposure and no significant demographic or laboratory covariates were identified. Based on the population PK model, assuming the PK is similar between healthy volunteers and moderate to severe UC patients, the dosing regimen of PRA023 1000 mg on Week 0/Day 1 followed by 500 mg on Weeks 2, 6, and 10 is expected to lead to a  $C_{max}$  (mean  $\pm$  SD) of [redacted]  $\pm$  [redacted]  $\mu\text{g/mL}$  and an  $AUC_{0-672hr}$  of [redacted]  $\pm$  [redacted]  $\mu\text{g}\cdot\text{hr/mL}$  after the last 500 mg induction dose.

Of note, the predicted  $C_{max}$  after the initial 1000 mg dose in the IP is expected to be the highest concentration obtained during the PR200-102 clinical dosing regimen. This level of exposure has already been evaluated in the 1000 mg SAD cohort of the healthy volunteer study (Study PR200-101). As stated, the highest exposure during the PR200-102 clinical dosing regimen based on AUC is expected to be after the last 500 mg induction dose due to accumulation with repeat dosing. The predicted AUC is expected to be approximately equivalent (within 10%) to that after the Phase 1 dosing regimen of 500 mg every other week.

From an induction efficacy perspective, assuming clearance of free soluble TL1A (sTL1A) from the gut will translate into efficacy, a physiologically based PK model was used to predict the impact of various dosing regimen of PRA023 on the level of sTL1A in normal and disease states in the central compartment (serum) and gut. The model predicts that the proposed induction regimen will lead to sTL1A levels of lower than healthy volunteers if the production level of sTL1A in the colon is as high as 60-fold.

After the 12-week induction, subjects who are in response will continue in the open-label extension randomized to 2 maintenance regimens. The maintenance regimen of 250 mg Q4W is selected to maintain the sTL1A level to below that of healthy volunteers if the production of sTL1A in the colon is up to 20X and the 100 mg Q4W regimen is selected to maintain the sTL1A level to below that of healthy volunteers if the production of sTL1A in the colon is up to 10X.

## 1.6 Overall Benefit/Risk Assessment

It is the hope that PRA023 will provide comparable or better efficacy than the currently approved biologic therapy, with an alternative and novel mechanism of action. There has been no safety signal identified based on nonclinical toxicity studies, safety analyses from normal healthy volunteers treated with up to 1000 mg of PRA023, and similar therapy in class. Based on the fact that PRA023 is a monoclonal antibody and an immunomodulatory agent, theoretical risks associated with treatment includes hypersensitivity reaction, infusion site reaction, and infections.

Since there is limited experience with use of PRA023, several steps will be taken to ensure that the benefit-risk relationship of study participation continues to be favorable throughout the study. In addition to ongoing safety monitoring of data throughout this study, a formal analysis is planned after all subjects have completed 12 weeks of treatment or early terminated from the study. Lastly, the study will be conducted under the aegis of an independent DMC which will perform safety and efficacy assessments at regularly scheduled times as well as on an ad hoc basis if needed, throughout this and a parallel open-label study in CD (PR200-103).

## 2 STUDY OBJECTIVES

### 2.1 Primary Objective

- To assess the safety and tolerability of PRA023 following 12-weeks of induction therapy
- To compare the efficacy of PRA023 vs placebo for induction of clinical remission at Week 12

### 2.2 Secondary Objectives

All objectives below refer to comparison of PRA023-treated subjects vs placebo-treated subjects in Cohort 1. For the objectives where the CDx status is a variable, a comparison of subjects in both Cohort 1 and Cohort 2 will be conducted.

- To compare the efficacy of PRA023 vs placebo for induction of endoscopic improvement at Week 12
- To compare the efficacy of PRA023 vs placebo for induction of clinical response at Week 12
- To compare the efficacy of PRA023 vs placebo in CDx+ subjects (Cohort 1 + Cohort 2) for induction of clinical remission at Week 12
- To compare the efficacy of PRA023 vs placebo for induction of symptomatic remission at Week 12
- To compare the efficacy of PRA023 vs placebo for induction of histologic remission at Week 12
- To compare the efficacy of PRA023 vs placebo for induction of histologic-endoscopic mucosal improvement at Week 12
- To compare the efficacy of PRA023 vs placebo in CDx+ subjects (Cohort 1 + Cohort 2) for induction of endoscopic improvement at Week 12
- To compare the efficacy of PRA023 vs placebo in CDx+ subjects (Cohort 1 + Cohort 2) for induction of clinical response at Week 12
- To compare the efficacy of PRA023 vs placebo in CDx+ subjects (Cohort 1 + Cohort 2) for induction of symptomatic remission at Week 12
- To compare the efficacy of PRA023 vs placebo in CDx+ subjects (Cohort 1 + Cohort 2) for induction of histologic remission at Week 12
- To compare the efficacy of PRA023 vs placebo in CDx+ subjects (Cohort 1 + Cohort 2) for induction of histologic-endoscopic mucosal improvement at Week 12
- To compare the efficacy of PRA023 in CDx+ (Cohort 1 + Cohort 2) vs CDx negative (CDx-) subjects for induction of clinical remission at Week 12

- To compare the efficacy of PRA023 vs placebo for induction of mucosal healing at Week 12
- To compare the efficacy of PRA023 vs placebo in CDx+ subjects (Cohort 1 + Cohort 2) for induction of mucosal healing at Week 12
- To compare the efficacy of PRA023 vs placebo for change in Inflammatory Bowel Disease Questionnaire (IBDQ) at Week 12
- To compare the efficacy of PRA023 vs placebo in CDx+ subjects (Cohort 1 + Cohort 2) for change in IBDQ at Week 12
- To compare the efficacy of PRA023 vs placebo in CDx+ subjects per alternative algorithm (Cohort 1 + Cohort 2) for induction of clinical remission at Week 12

### 2.3 Exploratory Objectives

- To assess the PK of PRA023 in subjects with UC over time
- To assess the effects of PRA023 on tissue and serum PD markers, including total TL1A concentrations over time
- To assess the effect of PRA023 on inflammatory biomarkers including fecal calprotectin and high sensitivity C-reactive protein (hsCRP) over time
- To assess the proportion of subjects in 3-component Modified Mayo Score response, 3-component Modified Mayo Score remission, endoscopic improvement, Robarts histopathology index (RHI) histologic remission, Geboes score histologic remission, and mucosal healing at Week 50
- To assess the change in Partial Mayo Score over time
- To assess the change in Geboes Index and RHI from Baseline to Week 12 and Week 50
- To assess the exposure-response relationship of PRA023 on PD markers over time
- To assess the proportion of subjects achieving corticosteroid-free-remission at Week 50
- To assess long-term safety, tolerability, and efficacy of PRA023

### 3 STUDY ENDPOINTS

The following will be measured for the evaluation of the study endpoints.

#### 3.1 Primary Objective Evaluation

- The proportion of subjects reporting adverse events (AEs), serious adverse events (SAEs), AEs leading to discontinuation, and markedly abnormal laboratory values.
- The proportion of subjects in the 3-component Modified Mayo Score clinical remission (as defined by endoscopic subscore of 0 or 1, rectal bleeding subscore of 0, and stool frequency subscore of 0 or 1 and not greater than Baseline) at Week 12. The 3-component Modified Mayo Score ranges from 0-9 and includes rectal bleeding, stool frequency and endoscopic assessment domains.

#### 3.2 Secondary Objective Evaluation

- The proportion of subjects with endoscopic improvement, as defined by endoscopy subscore  $\leq 1$  with no friability) at Week 12.
- The proportion of subjects in 3-component Modified Mayo Score clinical response at Week 12. The 3-component Modified Mayo Score clinical response is defined by reduction from Baseline  $\geq 2$  points and  $\geq 30\%$  in 3-component Modified Mayo Score, accompanied by a reduction  $\geq 1$  in rectal bleeding subscore or absolute rectal bleeding subscore  $\leq 1$ .
- The proportion of subjects in the 3-component Modified Mayo Score clinical remission (as defined by endoscopic subscore of 0 or 1, rectal bleeding subscore of 0, and stool frequency subscore of 0 or 1 and not greater than Baseline), in CDx+ subjects (Cohort 1 + Cohort 2) treated with PRA023 compared to CDx+ placebo-treated subjects at Week 12. The 3-component Modified Mayo Score ranges from 0-9 and includes rectal bleeding, stool frequency and endoscopic assessment domains.
- The proportion of subjects in symptomatic remission at Week 12.
- The proportion of subjects with histologic remission (defined Geboes score  $\leq 3.1$ ) at Week 12.
- The proportion of subjects with histologic-endoscopic mucosal improvement (defined as Geboes score  $\leq 3.1$  and endoscopy subscore  $\leq 1$  with no friability) at Week 12.
- The proportion of subjects with endoscopic improvement, as defined by endoscopy subscore  $\leq 1$  with no friability, in CDx+ subjects (Cohort 1 + Cohort 2) treated with PRA023 compared to CDx+ placebo-treated subjects at Week 12.
- The proportion of subjects in 3-component Modified Mayo Score clinical response in CDx+ subjects treated with PRA023 compared to CDx+ placebo-treated subjects at Week 12. The 3-component Modified Mayo Score clinical response is defined by reduction from Baseline  $\geq 2$  points and  $\geq 30\%$  in 3-component Modified Mayo Score,

- accompanied by a reduction  $\geq 1$  in rectal bleeding subscore or absolute rectal bleeding subscore  $\leq 1$ .
- The proportion of subjects with symptomatic remission in CDx+ subjects (Cohort 1 + Cohort 2) treated with PRA023 compared to CDx+ placebo-treated subjects at Week 12.
  - The proportion of subjects with histologic remission, defined as Geboes score  $\leq 3.1$ , in CDx+ subjects (Cohort 1 + Cohort 2) treated with PRA023 compared to CDx+ placebo-treated subjects at Week 12.
  - The proportion of subjects with histologic-endoscopic mucosal improvement (defined as Geboes score  $\leq 3.1$  **and** endoscopy subscore  $\leq 1$  with no friability), in CDx+ subjects (Cohort 1 + Cohort 2) treated with PRA023 compared to CDx+ placebo-treated subjects at Week 12.
  - The proportion of subjects with clinical remission (defined as endoscopic subscore of 0 or 1, rectal bleeding subscore of 0, and stool frequency subscore of 0 or 1 and not greater than Baseline) in CDx+ subjects (Cohort 1 + Cohort 2) treated with PRA023 compared to in CDx- subjects treated with PRA023 at Week 12.
  - The proportion of subjects with mucosal healing (defined as Geboes score  $\leq 2B.1$  **and** endoscopy subscore of  $\leq 1$ ) at Week 12.
  - The proportion of subjects with mucosal healing (defined as Geboes score  $\leq 2B.1$  **and** endoscopy subscore of  $\leq 1$ ), in CDx+ subjects (Cohort 1 + Cohort 2) treated with PRA023 compared to CDx+ placebo-treated subjects at Week 12.
  - The proportion of subjects with IBDQ response, as defined by  $\geq 16$ -point increase from Baseline at Week 12.
  - The proportion of subjects with IBDQ response, as defined by  $\geq 16$ -point increase from Baseline, in CDx+ subjects (Cohort 1 + Cohort 2) treated with PRA023 compared to CDx+ placebo-treated subjects at Week 12.
  - The proportion of subjects in the 3-component Modified Mayo Score clinical remission (as defined by endoscopic subscore of 0 or 1, rectal bleeding subscore of 0, and stool frequency subscore of 0 or 1 and not greater than Baseline), in CDx+ subjects per alternative algorithm (Cohort 1 + Cohort 2) treated with PRA023 compared to CDx+ placebo-treated subjects per alternative algorithm at Week 12. The 3-component Modified Mayo Score ranges from 0-9 and includes rectal bleeding, stool frequency, and endoscopic assessment domains.

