### 4.2.1 Inclusion/Exclusion Criteria

#### 4.2.1.1 Inclusion Criteria

Subjects are required to meet the following criteria in order to be included in the study:

1. Male or female  $\geq 18$  years of age.
2. Subjects must have had a diagnosis of UC at least 3 months before screening (confirmed by endoscopy + histology) to be eligible for study participation. For subjects with no documented confirmation of UC diagnosis or if previous diagnosis is not deemed conclusive, UC diagnosis must be confirmed at time of screening colonoscopy. Note that mention of “chronic inflammation” or “ulcerative colitis” or equivalent on histology report is acceptable.
3. Moderately to severely active UC as defined by 3-component Modified Mayo score (3 components of rectal bleeding, stool frequency, and endoscopy) of 4 to 9, inclusive, with Modified Mayo endoscopic subscore  $\geq 2$  **and** rectal bleeding subscore  $\geq 1$ .
4. Subjects must satisfy **at least one** of the following criteria:
  - a) **In the past**, had an inadequate response to **one or more** of the following treatments:
    - Oral prednisone  $\geq 40$  mg/day (or equivalent) or budesonide  $\geq 9$  mg/day or equivalent or beclomethasone  $\geq 5$  mg/day for at least 2 weeks
    - Corticosteroid dependence as defined by failed to successfully taper to  $< 10$  mg/day of prednisone or equivalent (i.e., had a flare of disease) within 3 months of starting therapy, or if relapse occurs within 3 months of stopping corticosteroids
    - Immunosuppressants (azathioprine  $\geq 2$  mg/kg/day or 6-mercaptopurine  $\geq 1.0$  mg/kg/day [or documentation of a therapeutic concentration of 6-thioguanine nucleotide]) for at least 8 weeks. Note: a lower dosage of 6-MP or AZA is acceptable if local guidelines specify a different treatment regimen (which would need be documented in the source document)
    - An approved anti-TNF agent at an approved labeled dose for at least 8 weeks
    - Vedolizumab at the approved labelled dose for at least 8 weeks
    - An approved JAK inhibitor (e.g., tofacitinib, upadacitinib, or filgotinib) at an approved labelled dose for at least 8 weeks

- An approved anti-IL-12/23 (e.g., ustekinumab) at an approved labelled dose for at least 8 weeks
- An approved sphingosine 1-phosphate receptor (S1PR) modulator (e.g., ozanimod) at an approved labelled dose for at least 12 weeks

**OR**

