#### 9.1.2 Full Analysis Set (FAS) Populations

The FAS population for Cohort 1: will be a subset of the Safety population and will include all subjects who have been randomized and treated in Cohort 1.

The FAS population for CDx+: will be all CDx+ subjects who are randomized and treated in both Cohort 1 and Cohort 2.

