1 INTRODUCTION

This statistical analysis plan (SAP) addendum describes the additions or modifications to the approved SAP V01 dated 10 August 2022 and is based on the study protocol version 4.0.

The SAP addendum covers the following topics of statistical analyses of the Induction Period for Cohort 1 following the corresponding database lock:

- Modification of Section 6.10, for the approach to multiplicity adjustment.
- Addition of an interim analysis for subjects with CDx+ based on protocol specified algorithm and the alternative algorithms.

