
 Proportion of subjects with histologic improvement (defined as Geboes score \leq 3.1) at Week 12 	Histology Analysis Set (0.025)

 Proportion of subjects with histologic-endoscopic mucosal improvement (defined as Geboes score \leq 3.1 and endoscopy subscore \leq 1 with no friability) at Week 12 	Histology Analysis Set (0.025)

 Proportion of subjects with IBDQ response, as defined by \geq 16-point increase from Baseline at Week 12 	FAS (0.025)

 Proportion of subjects in 3-component Modified Mayo Score clinical remission at Week 12 in CDx+ subjects (Cohort 1 + Cohort 2) 	CDx+ FAS (0.0245)

 Proportion of subjects with endoscopic improvement, as defined by endoscopy subscore \leq 1 with no friability) at Week 12 in CDx+ subjects (Cohort 1 + Cohort 2) 	CDx+ FAS (0.0245)

 Proportion of subjects in 3-component Modified Mayo Score clinical response at Week 12 in CDx+ subjects (Cohort 1 + Cohort 2) 	CDx+ FAS (0.0245)

 Proportion of subjects with symptomatic remission (as defined by rectal bleeding score = 0 and stool frequency score = 0) at Week 12 in CDx+ subjects (Cohort 1 + Cohort 2) 	CDx+ FAS (0.0245)

 Proportion of subjects with histologic-endoscopic mucosal healing (defined as Geboes score \leq 2B.1 and endoscopy subscore \leq 1 with no friability) at Week 12 in CDx+ subjects (Cohort 1 + Cohort 2) 	CDx+ Histology Analysis Set (0.0245)

 Proportion of subjects with histologic improvement (defined as Geboes score \leq 3.1) at Week 12 in CDx+ subjects (Cohort 1 + Cohort 2) 	CDx+ Histology Analysis Set (0.0245)

 Proportion of subjects with histologic-endoscopic mucosal improvement (defined as Geboes score \leq 3.1 and endoscopy subscore \leq 1 with no friability) at Week 12 in CDx+ subjects (Cohort 1 + Cohort 2) 	CDx+ Histology Analysis Set (0.0245)

 Proportion of subjects with IBDQ response, as defined by \geq 16-point increase from Baseline at Week 12 in CDx+ subjects (Cohort 1 + Cohort 2) 	CDx+ FAS (0.0245)

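### The stand-alone histologic endpoint has no baseline condition in the protocol, and the set that might supply one in the confirmatory test is not defined in the available text

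*Protocol*

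**What the plan says.** **Endpoint.** Protocol 3.2 gives "The proportion of subjects with histologic remission (defined Geboes score" at or below 3.1 at Week 12, and 6.4 repeats the cut-off. The matching objective in 2.2 is framed as induction: "To compare the efficacy of PRA023 vs placebo for induction of histologic remission at Week 12". SAP addendum Section 2, Table 1 keeps the cut-off under another name: "Proportion of subjects with histologic improvement (defined as Geboes score" at or below 3.1. None of these definitions refers to the screening biopsy.

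**Entry.** Protocol 4.2.1.1 requires "Moderately to severely active UC as defined by 3-component Modified Mayo score (3 components of rectal bleeding, stool frequency, and endoscopy") of 4 to 9, with endoscopic subscore at least 2 and rectal bleeding subscore at least 1. Histology serves only to confirm the diagnosis; a mention of chronic inflammation, ulcerative colitis "or equivalent on histology report is acceptable". No minimum Geboes score is set.

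**Population.** Under protocol 9.1.2 the Cohort 1 FAS "will include all subjects who have been randomized and treated in Cohort 1", and 9.3.2 estimates the Cohort 1 secondary endpoints in the FAS. Addendum Table 1 instead assigns this endpoint to "Histology Analysis Set (0.025"), and its CDx+ counterpart to a CDx+ Histology Analysis Set at 0.0245. Neither set is defined in the addendum, which by its own account "describes the additions or modifications to the approved SAP V01 dated 10 August 2022". SAP V01 is not among the documents.

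**Baseline histology.** Biopsies are taken at Screening and Week 12 (protocol 6.4.3). Change in Geboes from Baseline is exploratory only (3.3).

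**The concern.** A subject at or below 3.1 at screening who does not change has not been induced into anything, yet meets the definition. Every other test in addendum Table 1 is protected against this:

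- Clinical remission, endoscopic improvement and both histologic-endoscopic composites need an endoscopy subscore of 1 or less; entry needs 2 or more.
- Symptomatic remission needs a rectal bleeding subscore of 0; entry needs 1 or more.
- Clinical response and IBDQ response are changes from Baseline.

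Only the stand-alone histologic endpoint and its CDx+ counterpart could be met unchanged from entry.

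Its place in the sequence raises the stakes. In protocol 9.3.2 it is the fifth and last secondary endpoint in the chain, so a failure there costs only itself. In the addendum it is the sixth of 16 tests. A failure makes the ten that follow exploratory: two in Cohort 1 and all eight in CDx+ subjects.

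**Working it through.** **1. The plan's own figures.** Protocol 8.2 claims more than 80% power with 60 per arm at 1-sided 0.025, for 5% v 24% (primary) and 15% v 38% (endoscopic improvement). The check uses the unstratified pooled-variance normal approximation, without continuity correction:

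power = Φ{ [(p1 − p0) − 1.96·√(2p̄(1−p̄)/n)] / √([p0(1−p0) + p1(1−p1)]/n) }, where p̄ = (p0 + p1)/2.

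For 15% v 38%: (0.23 − 1.96 × 0.0806)/0.0778 = 0.926, so power is 82.3%. For 5% v 24% it is 84.9%. Both claims reproduce. The documents state no rate or power for the histologic endpoint.

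**2. Dilution model.** Let f be the share at or below 3.1 at screening, q the probability that such a subject is still there at Week 12, and r the rate among subjects above 3.1 at screening. Then

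p(arm) = (1 − f)·r(arm) + f·q.

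With the same q in both arms, the risk difference is (1 − f) times the difference in active subjects.

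**3. Inputs.** From the documents: 60 per arm, 1:1 allocation, 1-sided 0.025. Assumed: r = 15% v 38% (borrowed from the endoscopic improvement rates), q = 80% in both arms, and f from 0 to 20%. The restricted analysis has 60(1 − f) subjects per arm and the rates 15% v 38%.

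| f | Placebo, all | PRA023, all | Difference (points) | Power, all subjects | Power, baseline-active only (n per arm) |
|---|---|---|---|---|---|
| 0 | 15.00% | 38.00% | 23.00 | 82% | 82% (60) |
| 2% | 16.30% | 38.84% | 22.54 | 80% | 82% (58.8) |
| 5% | 18.25% | 40.10% | 21.85 | 76% | 80% (57) |
| 10% | 21.50% | 42.20% | 20.70 | 69% | 78% (54) |
| 20% | 28.00% | 46.40% | 18.40 | 55% | 73% (48) |

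Worked row, f = 10%: placebo 0.9 × 15 + 0.1 × 80 = 21.5%; PRA023 0.9 × 38 + 0.1 × 80 = 42.2%. Power in all subjects: (0.207 − 1.96 × 0.0851)/0.0829 = 0.486, giving 69%. Restricted: (0.23 − 1.96 × 0.0849)/0.0820 = 0.775, giving 78%.

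**4. Sensitivity to the active rates.** With 20% v 40% in active subjects, power is 67% at f = 0. In all subjects v baseline-active subjects it is 54% v 62% at f = 10% and 43% v 57% at f = 20%.

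**5. Sensitivity to equal persistence.** Suppose the drug also keeps baseline-low subjects low: q = 60% on placebo, 80% on PRA023. At 15% v 38%, power in all subjects v baseline-active subjects becomes 77.5% v 78.1% (f = 10%), 73.4% v 73.0% (20%) and 70.2% v 67.1% (30%). The gain from restricting vanishes and then reverses.

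**The case against.** The strongest objection is that the current plan does not test this endpoint in the FAS. Every histology row in Table 1 has its own analysis set, which suggests some histology condition. That could be active histology at baseline, or merely evaluable biopsies. A definition that sits in SAP V01 is not missing from the plan. This stands: a reader might infer that baseline-low subjects are counted as responders in the confirmatory test, and the documents do not show it.

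Second, f is probably low. Entry needs an endoscopic subscore of at least 2, which Appendix 16.1 describes as marked erythema, friability and erosions. Central subscores determine eligibility (6.4.2), and biopsies come from the most severely affected site, at the ulcer edge if ulcerated (6.4.3). This also stands. It makes the 20% row hard to credit, and at f = 2% the loss is about two points. It does not make f zero, and the documents give no figure.

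Third, the power gain rests on no drug effect in baseline-low subjects. Step 5 shows that this is correct. The case for a baseline condition then rests on the meaning of induction rather than on power.

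Two further inferences fail. With 1:1 randomization, equal extra successes in both arms do not inflate type I error or favour the drug. The histologic-endoscopic composites need no Geboes floor either: nobody can meet them at entry, so a floor would only discard subjects.

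**Conclusion.** The protocol gap is established. Sections 3.2, 6.4 and 9.3.2 together let a FAS subject who enters at or below 3.1 and does not change count as an induced success. Whether that carries into the confirmatory test is not established, because the Histology Analysis Set is undefined in the available text.

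If it does carry over, the consequence is a smaller risk difference, lost power at the sixth test in the chain, and a reported rate that does not describe induction. Under equal 80% persistence and 15% v 38%, the power difference between the two analyses runs from about 2 points at f = 2% to 9 at 10% and 18 at 20%. These figures are illustrative: f, the persistence and the histologic rates are all assumed, and the calculation ignores stratification. The point affects one stand-alone endpoint and its CDx+ counterpart.

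**What to change.** For the stand-alone histologic endpoint and its CDx+ counterpart only:

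- Run the confirmatory test in treated subjects with screening Geboes above 3.1, counting missing Week 12 histology as non-response.
- Give the all-subject result as a sensitivity analysis.
- Report the number at or below 3.1 at screening, by arm.
- If SAP V01's Histology Analysis Set already requires screening Geboes above 3.1, state that rule beside addendum Table 1 and align protocol 3.2, 6.4 and 9.3.2 with it.
- Leave the histologic-endoscopic composites unchanged.

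The cost is wording. Screening biopsies are already taken and sent to blinded central pathology, and baseline Geboes is needed anyway for the exploratory change endpoint. The downside is a somewhat smaller denominator for this test and its counterpart, for example 54 rather than 60 per arm in Cohort 1 at f = 10%.
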